# **ABACCuS Supplemental Serology Data Collection Form:**

Patient Initials/Study II	D:	Date of Enrollment:	
Plasma Unit Used:		Date and Time of Transfusion:	
Patient Serology	_ Weeks Post-Transfusion (+/- 1 d	ay)	
lgA OD:	lgG OD:	Date and Time of Specimen:	
Patient Serology	_ Weeks Post-Transfusion (+/- 1 d	ay)	
IgA OD:	lgG OD:	Date and Time of Specimen:	
Patient Serology	_ Weeks Post-Transfusion (+/- 1 d	ay)	
IgA OD:	lgG OD:	Date and Time of Specimen:	
Patient Serology	_ Weeks Post-Transfusion (+/- 1 d	ay)	
IgA OD:	lgG OD:	Date and Time of Specimen:	
Patient Serology	_ Weeks Post-Transfusion (+/- 1 d	ay)	
IgA OD:	lgG OD:	Date and Time of Specimen:	
Patient Serology	_ Weeks Post-Transfusion (+/- 1 d	ау)	
IgA OD:	lgG OD:	Date and Time of Specimen:	
Patient Serology	_ Weeks Post-Transfusion (+/- 1 d	ау)	
IgA OD:	lgG OD:	Date and Time of Specimen:	
Patient Serology	_ Weeks Post-Transfusion (+/- 1 d	ау)	
IgA OD:	lgG OD:	Date and Time of Specimen:	
Patient Serology	_Weeks Post-Transfusion (+/- 1 d	ay)	
IgA OD:	lgG OD:	Date and Time of Specimen:	
Signature of coordinate	or	 Date	
orginature or coordinate	OI.	Date	
Signature of Investigat	or reviewing data	 Date	

# ABACCuS SARS-CoV-2 RT PCR Data Collection Form:

Patient Initials/Study ID: _		Date of Enrollment:
Plasma Unit Used:		Date and Time of Transfusion:
Patient Qualifying RT PC	R:	
Result:	CT Value:	Date and Time of Specimen:
Patient Pre-Transfusion F	RT PCR:	
Result:	CT Value:	Date and Time of Specimen:
Patient 24 hour Post-Tran	nsfusion RT PCR:	
Result:	CT Value:	Date and Time of Specimen:
Patient 72 hour Post-Tran	nsfusion RT PCR:	
Result:	CT Value:	Date and Time of Specimen:
Patient 7 Days Post-Tran	sfusion RT PCR:	
Result:	CT Value:	Date and Time of Specimen:
Patient 14 Days Post-Tra	nsfusion RT PCR:	
Result:	CT Value:	Date and Time of Specimen:
Signature of coordinator		 Date
engination of occidentation		Dato
Signature of Investigator	reviewing data	Date

ABACCuS 28 Safety Form:					
Patient Initials/Study ID:	Date of Enrollment:				
Plasma Unit Used:	Date and Time of Transfusion:				
In the 2 hours after the transfusion: Did the patient have a rapid decline in respiratory status: Y	/N				
If yes: Date and Time:	Severity:				
If yes: Description of the event:					
Did the patient have a rapid decline in clinical status: Y/N					
If yes: Date and Time:	Severity:				
If yes: Description of the event:					
In the 4 hours after the transfusion: Did the patient have a fever of >38 $^{\circ}$ C: Y/N $T_{max}$ : _	If yes: Date and Time:				
Did the patient have an allergic reaction: Y/N  Conjunctival Edema: Y/N Edema of Oral Area: Y/N  Generalized Flushing: Y/N Hypotension: Y/N  Maculopapular Rash: Y/N Pruritus (itching): Y/N  Urticaria (hives): Y/N	Localized Angioedema: Y/N				
In the 6 hours after the transfusion: Was the patient diagnosed with Transfusion Associated Cir	rculatory Overload (TACO): Y/N				
If yes: Date and Time:	Severity:				
Was the patient diagnosed with Transfusion Related Acute	Lung Injury (TRALI): Y/N				
If yes: Date and Time:	Severity:				
In the 24 hours after the transfusion: Did the patient have evidence of cytokine storm: Y/N					
If yes: Date and Time:	Severity:				
If yes: Description of the event:					
Signature of coordinator	Date				
Signature of Investigator reviewing data	Date				

ABACCuS 28 Day Ou	tcome Form Gro	oup A:						
Patient Initials/Study ID:			Date of Enrollment:					
Plasma Unit Used:			Date a	Date and Time of Transfusion:				
Primary Outcome:								
Was the patient intuba	ted within 28 days	s of the transfus	ion: Y/N					
If intubated: Date of intubation:				Day #:				
Secondary Outcomes	5 :							
	Carron (1) No limitation	ig supplemental asive ventilation	O 2 or high flo	O (4) Req w O 2 device	luiring supp			
Cardio-circulatory an	` '	ys of transfusion	on: Y/N		If so c	late:		
Renal failure by RIFLE criteria within 28 days of trans				Y/N	If so c	date:		
	B days of transfu T or AST >5x three rsening of preex	ne upper limit c			If so o	late:		
Evidence of cytokine	storm based or	n inflammatory	markers:	Y/N	If so c	late:		
Days on ventilator: _	Days off	ventilator:	_ Days o	on coldflov	N:			
Days on CPAP:	Days on I	BIPAP:	Days o	Days on non-rebreather:				
Days on NC:	Days on I	Hiflo NC:	_ Discha	Discharge on new home O 2 : Y/N				
Requirement of pres	sor support: Y/N							
Pressors used	d and dates of u	se:						
In hospital mortality: Length of Stay: Readmission: Y/N	_ ICU Leng	days: Y/N th of Stay:	<del></del>			date:		
	55 4.49			<del> </del>	55 6			
Signature of coordinate	or			Date		-		

Date

Signature of Investigator reviewing data

ABACCuS Final Outcor	me Form Group A:		
Patient Initials/Study ID:		Date of Enrollment:	
Plasma Unit Used:		Date and Time of Transfusion:	
Primary Outcome:			
Was the patient intubated	d after the transfusion: Y/N		
If intubated: Da	ate of intubation:	Study Day #:	
Secondary Outcomes:			
O Hospitalized, O O	int ordinal scale: (1) No limitations on activities (3) Not requiring supplemental O (5) On non-invasive ventilation of (6) On invasive mechanical ventif (7) Deceased	$O(4)$ Re high flow $O_2$ devi	equiring supplemental O 2
Cardio-circulatory arrest after transfusion: Y/N		If so date:	
Renal failure by RIFLE criteria after transfusion: Y/N		If so date:	
	fusion: Y/N or AST >5x the upper limit of e ening of preexisting liver failure		If so date: AST of >25%: Y/N
Evidence of cytokine s	torm based on inflammatory m	arkers: Y/N	If so date:
Days on ventilator:	Days off ventilator:	Days on coldflo	ow:
Days on CPAP:	Days on BIPAP:	Days on non-rebreather:	
Days on NC: Days on Hiflo NC:		Discharge on new home O 2 : Y/N	
Requirement of presso	or support: Y/N		
Pressors used a	and dates of use:		
In hospital mortality: Y/Length of Stay: Readmission: Y/N		_	If so date:
Signature of coordinator		Date	
Signature of Investigator reviewing data		Date

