**UP: Unanticipated Problem** 

**Sample Size:** 500 (300 serious but non-intubated patients, 200 intubated patients)

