# **Secondary Objectives:**

 Cumulative incidence of serious adverse events during the study period: transfusion reaction (fever, rash), transfusion-related acute lung injury (TRALI), transfusion-associated circulatory overload (TACO), and transfusion-related infection.

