# 2.3 Study population

#### **Inclusion Criteria for Enrollment**

- 1. Subjects must be 18 years of age or older.
- 2. Hospitalized with confirmed COVID-19 infection via COVID-19 SARS-CoV-2 RT-PCR testing.
- 3. Symptoms consistent with COVID-19 infection (fever, acute onset cough, shortness of breath) at time of screening.
- 4. Patient requires >6L NC O2 (Group A) or intubated (Group B).
- 5. Patient (or their representative) is willing and able to provide written informed consent and comply with all protocol requirements.

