#### 2.4 Schedule of events

Study Period	Screening	Baseline	Treatment		Follow Up a					
Day	-1 to 0	0	0	D	1	3	7	14	21	28
Eligibility								,	,	
Inclusion/Exclusion	Х									
Informed consent	Х									
Demographics and	V									
medical history form	X									
Initial data collection	Х									
form	^									
Type and Screen	Х									
Pregnancy Test	Х									
Study Procedures										
Plasma transfusion			X							
Vital signs			Xp							
Physical exam c	X		Xd		Χ		Χ			
Daily vital signs, clinical										
and laboratory values				Χ						
form										
Daily medications form				Χ						
Adverse event		X	X	Х						
monitoring				^						
Serology collection form		X	X		Χ	Χ	Χ	Χ	Χ	Xe
Outcome form										Xf
Laboratory Testsg				_	•	,	,			•
CBC with differential		X		Χ						
CMP		Χ		Χ						
Ferritin		Χ		Χ						
Fibrinogen		Χ					Χ	Χ	Χ	Χ
CRP		Χ		Χ			Χ	Χ	Χ	Χ
ESR		Χ					Χ	Χ	Χ	Χ
Creatine Kinase		Χ					Χ	Χ	Χ	Χ
D-Dimer		Χ					Χ	Χ	Χ	Χ
LDH		Х					Χ	Χ	Χ	Χ
Interleukin-6		X					Χ	Χ	Χ	Χ
Triglycerides		Χ					Χ	Χ	Χ	Χ
Procalcitonin		Χ					Χ	Χ	Χ	Χ
Anti-SARS-CoV-2 IgA			X h		Χ	Χ	Χ	Χ	Χ	Xi
Anti-SARS-CoV-2 IgG			X h		Χ	Χ	Χ	Χ	Χ	Xi
SARS-CoV-2 RT PCR			Xj		Χ	Χ	Χ	Χ		

- a Column D are obtained daily, day 1 and 3 are obtained 24 hours (+/- 1 hour) from transfusion end, day 7, 14, 21, and 28 are obtained any time on that calendar day.
- b Standard vital signs for transfusion of blood products will be performed.
- c Given the issues with isolation and PPE, the exam of the attending physician's team or the pulmonary critical care team can be used.
- d Only if needed due to acute reaction.
- e After 28 days will be collected every 7 days +/- 1 day till discharge.
- f Outcome form to be filled out on final day of admission if prior to 28 days or at 28 days, after 28 days a second outcome form to be filled out on final day of admission, readmission will be tracked for 90 days.
- g All laboratory tests from this list which are obtained as standard of care will be tracked, baseline labs within 24 hours are acceptable and do not need to be reordered.
- h To be drawn within 1 hour prior to transfusion and 1 hour post-transfusion completion (no earlier than 1 hour but up to 75 min post transfusion).
- i After day 28 this will be drawn every 7 days +/- 1 day while participant remains hospitalized.
- j To be obtained within 1 hour prior to transfusion.

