#### 2.5 Treatment

All study participants will receive 1 unit of the study product. There is no re-dosing of the product within this study. There is no formal randomization, but both the patient and the study team will be blinded to the amount of anti-SARS-CoV-2 antibodies found in the unit of plasma assigned to the participant. The blind will be maintained until study closure and formal data analysis.

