#### **Known Risks of Plasma Transfusion**

Risks of any transfusion of plasma include: fever, chills, rash, headache, serious allergic reactions, TRALI, TACO, transmission of infectious agents.

The chances of any of these occurring are as follows:

Acute hemolytic reaction: 1 in 40,000 units transfused

Febrile transfusion reaction: 1 in 100 to 1 in 1000 units transfused

Urticarial reaction (hives): 1 in 100 units transfused Anaphylaxis: 1 in 20,000 to 1 in 50,000 units transfused

Transfusion related acute lung injury (TRALI): 1 in 1,200 to 1 in 190,000 units transfused

Transfusion related circulatory overload (TACO): less than 1 in 100 units transfused

Transmission of Hepatitis B: less than 1 in 250,000 units transfused Transmission of Hepatitis C: less than 1 in 1,000,000 units transfused

Transmission of HIV: less than 1 in 1,000,000 units transfused

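### The safety form records fever after plasma as any temperature above 38 C within 4 hours, with no pre-transfusion reading, so its incidence cannot be read as a febrile-reaction rate

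*Combined protocol and SAP*

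**What the plan says.** - **Safety form.** Under the 4-hour window of the ABACCuS 28 Safety Form, the fever item is "Did the patient have a fever of >38" C, answered Y/N, with a maximum temperature and a date and time. The item has no field for a temperature before the unit, for a change, or for cause. The neighbouring items are framed differently: TACO and TRALI are recorded as diagnoses, and the allergy item asks about an allergic reaction.
- **Source of safety data.** Section 2.2 points to this form for safety data.
- **Safety objective.** The Secondary Objectives in section 2.1 give a cumulative incidence of serious adverse events and list under it "transfusion reaction (fever, rash").
- **Entry.** Inclusion criterion 3 in section 2.3 reads "Symptoms consistent with COVID-19 infection (fever, acute onset cough, shortness of breath) at time of screening".
- **Stated risk.** Section 4.1, Known Risks of Plasma Transfusion, gives "Febrile transfusion reaction: 1 in 100 to 1 in 1000 units transfused".
- **Exposure.** Section 2.5 says "All study participants will receive 1 unit of the study product". The planned sample is "500 (300 serious but non-intubated patients, 200 intubated patients").
- **Temperatures taken elsewhere.** Section 2.4, footnote b: "Standard vital signs for transfusion of blood products will be performed". The Initial Data Collection Form, completed at screening, takes current, maximum and minimum temperature over 24 hours. The daily form takes the maximum and minimum for each calendar day.
- **Adverse event rules.** The Adverse Events section treats a condition present at screening as baseline unless it worsens, and has each event graded for its relationship to treatment.

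No section defines a febrile transfusion reaction relative to a baseline temperature.

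**The concern.** A fixed threshold after the unit cannot separate a reaction to plasma from a fever the patient already had. Someone at 38.6 C before the transfusion and 38.4 C after it has cooled, yet the truthful answer on the form is Yes. In this population that case is not remote, since fever is one of the signs by which patients qualify.

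The design removes the usual remedy. In a trial with an untreated arm, background fever could be subtracted by comparison. Here everyone receives plasma, so the available correction is each patient's own temperature just before the unit, and the safety form does not ask for it.

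At stake is how one component of the secondary safety objective is interpreted. If form entries were tabulated as they stand, the figure would mix disease fever with reactions in unknown proportion and could not be set beside the risk stated in section 4.1.

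**Working it through.** The plan states no expected number of febrile reactions and no background fever rate, so there is no figure to reproduce. The check asks how much background fever it takes for the item to be dominated by disease.

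**Inputs**
- N = 500 patients, one unit each (sample size statement; section 2.5).
- r = true febrile-reaction risk per unit = 0.001 to 0.01 (section 4.1).
- b = share of patients above 38 C in the 4-hour window for reasons other than a reaction. This is not in the documents. It is an assumption, varied from 0.5% to 20%.

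**Step 1. Expected true reactions, N x r**
- All patients: 500 x 0.001 = 0.5 to 500 x 0.01 = 5.
- Group A: 300 x 0.001 = 0.3 to 300 x 0.01 = 3.
- Group B: 200 x 0.001 = 0.2 to 200 x 0.01 = 2.
- Chance of at least one among 500, 1 - (1 - r)^500: 0.39 to 0.99.

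**Step 2. Share of Yes answers that are background fever**

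Treat the two causes as independent, and count a patient with background fever as background. Then P(Yes) = b + r(1 - b), and the background share is b / (b + r(1 - b)).

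| Assumed b | Share at r = 1 in 100 | Share at r = 1 in 1000 | Expected Yes among 500 (r = 1 in 1000 to 1 in 100) |
|---|---|---|---|
| 0.5% | 33% | 83% | 3.0 to 7.5 |
| 1% | 50% | 91% | 5.5 to 10.0 |
| 5% | 84% | 98% | 25.5 to 29.8 |
| 10% | 92% | 99% | 50.5 to 54.5 |
| 20% | 96% | 99.6% | 100.4 to 104.0 |

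Example: b = 5%, r = 1% gives 0.05 / (0.05 + 0.01 x 0.95) = 0.05 / 0.0595 = 0.84. If patients with both causes are counted as reactions instead, this becomes 0.05 x 0.99 / 0.0595 = 0.83, so the attribution rule hardly matters.

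**Step 3. Break-even**

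Setting the share to one half gives b = r / (1 + r):
- r = 0.001: b = 0.10%.
- r = 0.01: b = 0.99%.

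Above these values, background fevers outnumber true reactions.

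**Step 4. Do other rules already remove background fever?**
- The adverse event baseline is fixed at screening, day -1 to 0 in section 2.4, and not at the start of transfusion. A patient without fever at screening who becomes febrile from COVID-19 before or after the unit is not screened out by it.
- Relationship grading could set such a fever aside, but no text says that a Yes on the safety form is graded before it is counted.
- The 24-hour temperatures on the initial form need not include the reading just before the unit. The daily form is tied to the calendar day.
- The transfusion vital signs in footnote b should supply the needed reading, but the safety form does not capture it and section 3.1 has no rule that uses it.

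**The case against.** The strongest reply is that the form records a fact and does not call it a reaction. The objective concerns serious adverse events, and a temperature of 38.4 C alone would not ordinarily meet the Serious Adverse Events definition. The baseline and relationship rules would then exclude a fever already present at screening or judged unrelated. Most of the temperatures needed for a rise-based reading are taken somewhere, so it might be reconstructed at analysis.

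Much of this stands. No text says that a Yes is tallied directly. But the same objective names fever and rash, which are seldom serious, as the reactions to be counted, so the documents leave open what the numerator is. Nor do they link the form to the rules that might clean it.

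Three stronger readings are tempting, and the documents do not support them:
- **That most counted reactions will be COVID-19 fever.** This is plausible, given the low break-even, but it needs a background rate that the documents do not give. Fever is one of three listed symptoms and is not required of everyone. Group A may enter up to 14 days after admission and Group B at any time after intubation. Discretionary acetaminophen (section 2.7) may suppress fever from either cause.
- **That the apparent incidence will be 10 to 40 times the stated upper risk.** That follows only if 10% to 40% of patients are febrile in the window, which is pure assumption.
- **That the form hides a relation between unit IgG and febrile reactions.** Background fever unrelated to IgG would dilute one. At b = 10%, a doubling of r from 1% to 2% moves the flagged rate only from 10.9% (0.10 + 0.90 x 0.01) to 11.8% (0.10 + 0.90 x 0.02). But with 0.5 to 5 true reactions expected, such a relation is barely estimable under any definition.

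**Conclusion.** The point holds in a limited form. The fever item has no baseline reference, there is no untreated arm, and the item is not tied to the attribution rules, so its incidence cannot be taken as a febrile-reaction rate or set against the risk in section 4.1. The size depends on an unknown background fever rate. What can be said from the protocol's own reaction risk is that a background of roughly 0.1% to 1% is enough for disease fever to predominate, and that assumed rates of 5% and 10% would make it at least about 84% and 92% of Yes answers. These figures assume that the section 4.1 risk applies to this plasma and that the two causes of fever are independent.

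Importance is low to moderate. The primary efficacy endpoints and the two primary safety endpoints do not use this item, and fever is not a named halting criterion.

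**What to change.** 1. Add the last temperature before the unit, with its time, to the safety form.
2. Define a febrile reaction as a temperature above 38 C with a prespecified rise from that reading. A rise of at least 1 C is one example. It is not taken from the documents, and the sponsor may choose another, provided that it is fixed before the antibody blind is lifted.
3. Report fever above 38 C without such a rise on a separate line.
4. State how a form entry passes through the Adverse Events and Serious Adverse Events sections before it is counted under the Secondary Objectives, and whether a non-serious fever belongs in that count at all.

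The cost is one form field and a short definition. The reading should already exist under the transfusion vital signs, so for patients already enrolled it may be retrievable from the medical record. The downside is that a blunted reaction in a patient who is already febrile, or who was pretreated with acetaminophen, may not meet the rise. It can still be reported as an adverse event.
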